### **Infusion Interruption**

Significant events requiring a change in treatment will be managed by immediate infusion interruption:

- The subject experiences a DLT as defined in Section [6.2.1.4](#)
- The subject experiences a clinically relevant grade 4 adverse event related to IP (see above)
- The subject experiences a grade  $\geq 2$  cytokine release syndrome that does not respond to medical management as described in [Table 7](#)
- The subject meets criteria for discontinuation of IP as described in Section [8.3](#)
- Technical problem with the infusion pump
- The investigational product is incorrectly prepared or administered (eg, overdose)

### **Restarting the Infusion**

Treatment may resume if the interruption is  $\leq 21$  days and if:

- The interruption occurred due to other reasons than toxicity (disease-related events, technical or logistic reasons; eg, diagnostic measurements). The infusion can be restarted at the same dose and without additional measures.
- The toxicity has resolved to CTCAE grade  $\leq 1$  (in case of dose reduction, infusion may be restarted without prior resolution of the toxicity to CTCAE grade  $\leq 1$  at the investigator's discretion)

Please also refer to specific guidance on restart after cytokine release syndrome in Section [6.6](#). Restarting the infusion after a treatment interruption requires care. The start should be performed in the hospital, under supervision of the investigator, if the reason for the interruption was other than a technical issue or the interruption exceeded 4 hours independent of reason. Assessments should be performed after infusion restart depending on the length of the interruption and the visit day on which the interruption occurred as described in the table below. The subject should be hospitalized for at least 48 hours after restart of the infusion.

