#### **6.2.1.5 Dosage Adjustments, Delays, Rules for Withholding or Restarting, Permanent Discontinuation**

##### **Criteria for Dose Delay or Dose Reduction**

Any clinically relevant (as determined by the investigator) grade 4 adverse event related to IP that does not meet the DLT criteria should lead to a dose delay and/or a dose reduction. The decision if a dose delay or reduction will be performed is up to the investigator's discretion. The sponsor may be consulted.

In case of grade 2 cytokine release syndrome, treatment can be continued on the currently tested dose level for 8 hours. If symptoms do not improve to grade 1, the dose will be de-escalated by 50% for an additional 24 hours. If CRS grade 2 resolves to grade 1, the dose can be re-escalated back to the level being tested. If symptoms persist, AMG 330 will be interrupted until symptoms improve to grade 1. If treatment is interrupted for < 24 hours, the interrupted dose can be resumed and re-escalated back to the tested dose level. If treatment is interrupted for > 24 hours, restart or repeat rules apply (see below).

In case of grade 3 cytokine release syndrome, treatment must be interrupted. The Amgen medical monitor has to be consulted prior to a planned restart.

In case of grade 4 cytokine release syndrome, treatment must be permanently discontinued. See Section [6.6](#) for specific instructions for the management of cytokine release syndrome.

Dose delay: treatment should be interrupted until the event is resolved to grade  $\leq 1$ , and can then be resumed at the same dose unless the interruption lasted for more than 24 hours, please see below. (Note: if the event needs > 21 days to resolve, treatment has to be permanently discontinued, see also below).

Dose reduction: treatment may be resumed after the event is resolved to grade  $\leq 1$  or immediately at the investigator's discretion at the previous (lower) dose level.

Re-escalation to the target dose can be considered if the event has resolved to  $\leq$  grade 1 if applicable.

In case of re-appearance of the same grade 4 adverse event, IP should be permanently discontinued.

For persistent or re-occurring clinically relevant grade 3 adverse event related to IP, a dose delay or a dose reduction should be considered.

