**Table 6. Assessments to be Performed After Infusion Interruption and Restart**

Length of Cycle	Length of Infusion Interruption	Dose level at which interruption occurred	Assessments to be performed
2 weeks	≤ 24 hours	Run-in dose, dose step or target dose	Continue following schedule of assessments per protocol
	> 24 hours	Run-in dose, dose step or target dose	Repeat the cycle and schedule of assessments ( Table 8 or Table 9 ) starting at day 1, perform dose step assessments as needed per Table 14
3 or 4 weeks	≤ 24 hours	Run-in dose, dose step or target dose	Continue following schedule of assessments per protocol
	> 24 hours < 7 days	Run-in dose or step dose	Repeat the cycle and schedule of assessments ( Table 9 – Table 23 ) starting at day 1, perform dose step assessments as needed per Table 14
	> 24 hours but < 7 days	Target dose	Consult with Sponsor regarding which visit days should be performed ( Table 9 – Table 23 ), perform dose step assessments as needed per Table 14a
	≥ 7 days	Run-in dose, dose step or target dose	Repeat the cycle and schedule of assessments ( Table 9 – Table 23 ) starting at day 1, perform dose step assessments as needed per Table 14

a If treatment is interrupted towards the end of cycle 1 after the target dose is reached, and the decision is made to not restart the infusion prior to day 29, only perform EOI assessments on Cycle 1 Day 29

In case of an infusion interruption of > 24 hours, regardless of the reason for interruption, restart of the infusion should be performed at the initial MTD (run in dose) and dose steps should be performed prior to administering the target dose. The dose level for each step and number of steps should be determined in consultation with the Sponsor prior to re-initiation of the infusion.

After two unsuccessful restarts, the subject will be considered as not DLT evaluable (if no DLT has been observed during treatment) and can be replaced. The subject may remain on the study and continue treatment with a previously tested target dose that has been well tolerated.

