Dexamethasone (8 mg IV) should be administered within 1 hour prior to restart and within 1 hour prior to the dose step(s). The subject should be hospitalized starting from restart of infusion until 72 hours after the dose step. After the dose step, assessments of vital signs, pulse oximetry and clinical evaluation should be performed as per the schedule of assessments for dose steps ([Table 14](#)).

The number of days of infusion at the target dose before and after an interruption should sum up to the planned duration, ie, minimum 10 days at the target dose for a 14 day

cycle, and minimum 14 days at the target dose for a 21 or 28 day cycle. In this case, the subject would still be DLT-evaluable. However, if the cycle was interrupted for more than 7 days, a new cycle should be started and the interrupted cycle would not be evaluable for DLT, unless the event that lead to the interruption was a DLT.

Please refer to the table below to determine the minimum duration of treatment for a subject to be counted as DLT evaluable.

**Note:** In case a treatment cycle is considered complete but lasted less than the planned number of days (14, 21, or 28, as applicable), the EOI bone marrow assessment should be performed once it was confirmed that the cycle will not be resumed in order to assess treatment response and determine the infusion-free interval prior to start of the next cycle, if applicable. Bone marrow and blood samples (for [REDACTED], immune cells, and plasma biomarker testing) should also be sent to the applicable central laboratories.

Planned Treatment Duration	Minimum Duration of Treatment at Target Dose to be Counted as DLT evaluable
2 weeks	7 days at target dose
3 weeks	14 days at target dose
4 weeks	14 days at target dose

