### 6.3 Other Protocol-required Therapies

All other protocol-required and recommended therapies including corticosteroids, that are commercially available are not provided or reimbursed by Amgen (except if required by local regulation). The investigator will be responsible for obtaining supplies of these therapies. Please also refer to Section 6.5.

**Dexamethasone:** Premedication with dexamethasone is required prior to each AMG 330 treatment cycle and prior to each dose step for the prevention of CRS (Exception: see instructions for dexamethasone use in Groups 4 and 5).

Dexamethasone should be administered as a single IV dose (8 mg) within 1 hour of start of infusion or dose step, respectively.

In the case of restart of infusion after an infusion interruption of > 24 hours, dexamethasone (8 mg IV) should be administered within 1 hour prior to restart and within 1 hour prior to the dose step.

For administration of dexamethasone after occurrence of CRS, follow guidance in Section 6.6 below.

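### The non-toxicity restart bullet in Protocol 6.2.1.5 lacks the 24-hour limit and so contradicts the run-in, dose-step and dexamethasone rule later in the same section

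*Protocol*

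**What the plan says.** Section 6.2.1.5, under Restarting the Infusion, sets one overall condition: treatment may resume if the interruption lasted no more than 21 days. Two bullets follow. The one for interruptions not caused by toxicity (disease-related, technical or logistic) says "The infusion can be restarted at the same dose and without additional measures". It has no other time limit and no cross-reference.

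The text after Table 6 in the same section says "In case of an infusion interruption of > 24 hours, regardless of the reason for interruption, restart of the infusion should be performed" at the run-in dose, with dose steps before the target dose. It adds "The dose level for each step and number of steps should be determined in consultation with the Sponsor prior to re-initiation of the infusion". Section 6.6 repeats the rule.

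On premedication, Section 6.3 says "In the case of restart of infusion after an infusion interruption of > 24 hours, dexamethasone (8 mg IV) should be administered" before the restart and again before the dose step, with an exception for the dexamethasone instructions of Groups 4 and 5. Section 6.2.1.5 gives the same two dexamethasone doses and adds "The subject should be hospitalized starting from restart of infusion until 72 hours after the dose step".

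The dose-delay paragraph earlier in Section 6.2.1.5, which covers toxicity, does carry the limit: treatment "can then be resumed at the same dose unless the interruption lasted for more than 24 hours, please see below".

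**The concern.** For a non-toxicity interruption longer than 24 hours but no longer than 21 days, one sentence permits the interrupted dose with nothing added, while another requires the run-in dose, steps, steroid and a longer stay. The interrupted dose may be the full target dose.

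The measures left out are protections against cytokine release syndrome (CRS). CRS is an identified risk in Table 2, and Section 6.6 warns that it can be fatal. Section 3.1.1 gives prevention of cytokine release as the reason for the steroid dose before a step. The bullet comes first and reads as a plain permission. The overriding rule sits after a table whose title concerns assessments, not dosing, so a site handling a pump or supply failure could stop reading too early.

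**Working it through.** The plan states no figure on this point, so the check is a comparison of the text, plus one short calculation of the hospital time at issue.

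**Side by side, for a non-toxicity interruption over 24 hours and up to 21 days**

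| Element | Bullet under Restarting the Infusion | Rule for over 24 hours | Source of the rule |
|---|---|---|---|
| Restart dose | Same dose | Run-in dose | 6.2.1.5 after Table 6; 6.6 |
| Dose steps | None | Required before target dose | 6.2.1.5 after Table 6; 6.6 |
| Dexamethasone | None | 8 mg IV before restart and before each step (Groups 4 and 5 excepted) | 6.2.1.5; 6.3 |
| Hospital stay | No addition; general 48-hour rule follows the bullets | From restart until 72 hours after the step | 6.2.1.5 |

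At 24 hours or less the two texts agree on dose, steps and dexamethasone.

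**Which rule is intended.** The later rule applies regardless of reason, which leaves no room for a non-toxicity exemption. The dose-delay paragraph and the grade 2 CRS paragraph both divide at 24 hours, and so does Table 6 for every cycle length. The bullet is out of line with all of these.

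**What else would stop a literal reading.**
- Table 6 has four rows for interruptions over 24 hours. All four say "perform dose step assessments as needed per" Table 14.
- Three of the four say to repeat the cycle and its assessments from day 1.
- The fourth row (3- or 4-week cycle, target dose, under 7 days) requires only Sponsor consultation on visit days. Protection is thinnest here, and this is where a same-dose restart means the full target dose.
- Directly after the bullets, Section 6.2.1.5 requires in-hospital restart when the interruption exceeded 4 hours, whatever the reason, and at least 48 hours in hospital afterwards.

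**Hospital time lost.** Inputs: stay until 72 hours after the step (6.2.1.5); 48-hour stay that still applies (6.2.1.5); run-in of 1 to 5 days (3.1.1, Group 1, assumed to apply at restart); one dose step (assumed).

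Stay under the over-24-hour rule = run-in + 72 h. Shortfall = that stay − 48 h.
- Run-in 1 day: 24 + 72 = 96 h; 96 − 48 = 48 h, or 2 days.
- Run-in 5 days: 120 + 72 = 192 h; 192 − 48 = 144 h, or 6 days.

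**Dexamethasone lost**, outside Groups 4 and 5, with one step: (1 at restart + 1 at step) × 8 mg = 16 mg.

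**The case against.** The strongest reply is that the protocol already settles the matter. The phrase about any reason for interruption is aimed at exactly the causes listed in the bullet, Section 6.6 repeats it, and Section 6.3 ties dexamethasone to the 24-hour trigger with no exception by cause. The neighbouring toxicity bullet also omits the 24-hour limit and relies on text elsewhere. A site would usually have to miss several instructions: Sponsor consultation, the Table 6 cycle repeats, the direction to start a new cycle after more than 7 days, and in-hospital restart.

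Most of this stands, and it limits the point to a wording error. It does not remove the error. The toxicity bullet does not affirmatively permit the same dose with nothing added; this one does. Sponsor consultation on steps helps only if the site recognises that steps are needed.

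Three stronger readings are tempting, and the documents do not support them:
- A reader might infer that the restart dose is unresolved, or that non-toxicity interruptions are deliberately exempt. The wording of the later rule excludes both.
- A reader might count the whole 4 to 8 day stay as lost. The 48-hour stay required after the bullets still applies, so only the excess counts.
- A reader might note that the conflict spans 20 of the 21 permitted days and take this as a measure of how often it arises. The documents give no frequency, and several of the bullet's examples suggest short pauses.

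**Conclusion.** The bullet is wrong as written for interruptions over 24 hours. Followed literally, it drops the run-in dose, the dose steps, the dexamethasone premedication and about 2 to 6 days of hospital observation beyond the 48 hours already required. That range rests on one dose step and on the 1 to 5 day run-in of Group 1 applying at restart. The intended rule is clear from the rest of the section and the partial safeguards are real, so this is a correction of wording in a safety-relevant instruction, not a gap in the dosing design.

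A reader might also infer that a mistaken full-dose restart would distort dose-limiting toxicity counts. That is possible in principle, but nothing in the documents allows it to be sized. No sample size, endpoint or analysis figure changes.

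**What to change.** Limit the bullet to interruptions of 24 hours or less and add: *For interruptions over 24 hours, regardless of reason, restart at the run-in dose with dose steps and CRS premedication as described after Table 6 (for Groups 4 and 5, per their premedication rules); the in-hospital restart rule below still applies.*

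The 48-hour stay and the handling of brief planned pauses need no change for this purpose. The cost is a sentence or two of protocol wording, with no effect on design, data collection or analysis. SAP Section 10 already anticipates a Protocol Amendment 10, which could carry it.

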**Table 6. Assessments to be Performed After Infusion Interruption and Restart**

Length of Cycle	Length of Infusion Interruption	Dose level at which interruption occurred	Assessments to be performed
2 weeks	≤ 24 hours	Run-in dose, dose step or target dose	Continue following schedule of assessments per protocol
	> 24 hours	Run-in dose, dose step or target dose	Repeat the cycle and schedule of assessments ( Table 8 or Table 9 ) starting at day 1, perform dose step assessments as needed per Table 14
3 or 4 weeks	≤ 24 hours	Run-in dose, dose step or target dose	Continue following schedule of assessments per protocol
	> 24 hours < 7 days	Run-in dose or step dose	Repeat the cycle and schedule of assessments ( Table 9 – Table 23 ) starting at day 1, perform dose step assessments as needed per Table 14
	> 24 hours but < 7 days	Target dose	Consult with Sponsor regarding which visit days should be performed ( Table 9 – Table 23 ), perform dose step assessments as needed per Table 14a
	≥ 7 days	Run-in dose, dose step or target dose	Repeat the cycle and schedule of assessments ( Table 9 – Table 23 ) starting at day 1, perform dose step assessments as needed per Table 14

a If treatment is interrupted towards the end of cycle 1 after the target dose is reached, and the decision is made to not restart the infusion prior to day 29, only perform EOI assessments on Cycle 1 Day 29

In case of an infusion interruption of > 24 hours, regardless of the reason for interruption, restart of the infusion should be performed at the initial MTD (run in dose) and dose steps should be performed prior to administering the target dose. The dose level for each step and number of steps should be determined in consultation with the Sponsor prior to re-initiation of the infusion.

After two unsuccessful restarts, the subject will be considered as not DLT evaluable (if no DLT has been observed during treatment) and can be replaced. The subject may remain on the study and continue treatment with a previously tested target dose that has been well tolerated.

Dexamethasone (8 mg IV) should be administered within 1 hour prior to restart and within 1 hour prior to the dose step(s). The subject should be hospitalized starting from restart of infusion until 72 hours after the dose step. After the dose step, assessments of vital signs, pulse oximetry and clinical evaluation should be performed as per the schedule of assessments for dose steps ([Table 14](#)).

The number of days of infusion at the target dose before and after an interruption should sum up to the planned duration, ie, minimum 10 days at the target dose for a 14 day

cycle, and minimum 14 days at the target dose for a 21 or 28 day cycle. In this case, the subject would still be DLT-evaluable. However, if the cycle was interrupted for more than 7 days, a new cycle should be started and the interrupted cycle would not be evaluable for DLT, unless the event that lead to the interruption was a DLT.

Please refer to the table below to determine the minimum duration of treatment for a subject to be counted as DLT evaluable.

**Note:** In case a treatment cycle is considered complete but lasted less than the planned number of days (14, 21, or 28, as applicable), the EOI bone marrow assessment should be performed once it was confirmed that the cycle will not be resumed in order to assess treatment response and determine the infusion-free interval prior to start of the next cycle, if applicable. Bone marrow and blood samples (for [REDACTED], immune cells, and plasma biomarker testing) should also be sent to the applicable central laboratories.

Planned Treatment Duration	Minimum Duration of Treatment at Target Dose to be Counted as DLT evaluable
2 weeks	7 days at target dose
3 weeks	14 days at target dose
4 weeks	14 days at target dose

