**Table 5. 3+3 Dose Level Decision Rules**

# Subjects a	#Subjects with DLT	Decision
3	1	Enroll 3 additional subjects at same dose level
3	0	Escalate b
3	≥ 2	De-escalate c
6	1	Escalate b
6	≥ 2	De-escalate c

[figure not shown]
a Subjects who are not DLT-evaluable (see Section 3.4) are excluded from the count of subjects

b If final dose level has been reached, accrual will be suspended.

c If 6 subjects already entered at next lower dose level, the estimated MTD has been established.

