### 3.4 Replacement of Subjects

Ineligible subjects (ie, subjects who were exposed to investigational product [IP] but post hoc were found to be ineligible) may be replaced. During dose escalation, subjects that are not DLT-evaluable will be replaced. A subject is not DLT-evaluable if he/she drops out of cycle 1 before completion of the DLT window for reasons other than an adverse event related to study drug **or the subject has not received IP treatment for at least 14 days at the target dose for a 3- or 4-week cycle or at least 7 days at a target dose for a 2-week cycle**. Following drug interruptions, if a subject is unable to

complete 2 repeat cycles for reasons other than DLT, the subject will not be DLT evaluable and can be replaced. All available safety data for subjects who are not DLT evaluable will still be evaluated and considered in DLRM decisions. No dose escalation will occur unless at least 3 subjects have **been assessed as DLT evaluable**.

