### DLT Evaluation

A subject is not DLT-evaluable if he/she drops out before completion of the DLT window for reasons other than an adverse event related to study drug **or the subject has not received IP treatment for at least 14 days at the target dose for a 3- or 4-week cycle or at least 7 days at a target dose for a 2-week cycle**. All available safety data for subjects who are not DLT evaluable will still be evaluated and considered in DLRM decisions. No dose escalation will occur unless at least 3 subjects have **been assessed as DLT evaluable**. Duration of a cycle might be extended and be different from the duration of the DLT window. For all cohorts, the DLT window may also be extended

retrospectively to assess events starting or persisting outside the window in case the DLT definition is time dependent (eg, in case of neutropenia, see below).

Any adverse event occurring outside the DLT window that is determined by the investigator to be possibly related to the investigational product, which is seen more frequently or is more severe than expected or is persistent despite appropriate management, can be determined to be a DLT upon unanimous decision by the DLRT after review of the adverse event and all available safety data.

Events listed below are to be considered as DLTs and exceptions when occurring in a subject during the DLT window unless clearly attributable to causes other than AMG 330 treatment:

- Any treatment-related death.
- Grade 4 neutropenia lasting  $\geq$  42 days from start of cycle in absence of evidence of active AML (in case of 3 or 4 weeks treatment cycles, the number of days would increase accordingly)
- Grade 3–5 non-hematologic toxicity not clearly resulting from the underlying leukemia EXCEPT:
  - Alopecia
  - Grade 3 fatigue, asthenia, fever, anorexia, or constipation
  - Grade 3 nausea, vomiting or diarrhea not requiring tube feeding, total parenteral nutrition, or requiring or prolonging hospitalization
  - Infection, bleeding, or other expected direct complication of cytopenias due to active underlying leukemia
  - Grade 3 infusion reaction, if successfully managed and which resolves within 72 hours
  - Grade 3 rash
  - Grade 3 or 4 tumor lysis syndrome if it is successfully managed clinically and resolves within 7 days without end-organ damage.

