- Grade 3 or 4 isolated electrolyte abnormalities (ie, those occurring without clinical consequence) that resolve, with or without intervention, to  $<$  Grade 2 levels in  $<$  72 hours will not be considered DLT.
- Grade 3 or 4 asymptomatic enzyme elevations including AST, ALT (without bilirubin elevation), GGT (gamma-glutamyl transferase), lipase and amylase that resolve to  $\leq$  Grade 2, with or without intervention, within 7 days will not be considered a DLT.
- CRS meeting any of the criteria listed below:
  - Grade 2 CRS that does not resolve, with or without intervention to Grade 1 within 7 days will be considered a DLT
  - Grade 3 CRS that does not resolve, with or without intervention to  $\leq$  Grade 2 within 5 days, or  $\leq$  grade 1 within 7 days, will be considered a DLT

- Grade 3 CRS reported at the initial dose (ie, at MTD1; applicable only after MTD1 has been defined) will be considered a DLT
- Grade 4 CRS occurring during AMG 330 treatment.
- Two separate grade 3 CRS events will be considered a DLT.

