6.2 Dose Limiting Toxicity Evaluable Analysis Set

The DLT-evaluable Analysis Set includes all DLT-evaluable subjects. The analysis of DLT will be restricted to the DLT-evaluable Analysis Set. A subject is not DLT-evaluable if he/she drops out before completion of the DLT window for reasons other than an adverse event related to study drug or the subject has not received IP treatment for at least 14 days at the target dose for a 3- or 4-week cycle or at least 7 days at a target dose for a 2-week cycle. Furthermore, following drug interruptions, if a subject is unable to complete 2 repeat cycles for reasons other than DLT, the subject will not be DLT evaluable.

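### Subjects who fail two restarts because of AMG 330 toxicity short of a DLT leave the DLT count and can be replaced, and no planned table or sensitivity estimate shows the effect on dose decisions

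*Protocol*

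**What the plan says.** Three clauses decide who is DLT-evaluable.

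- **Dropout.** Protocol Sections 3.4 and 6.2.1.4 and SAP Section 6.2 exclude a subject who "drops out before completion of the DLT window for reasons other than an adverse event related to study drug". Leaving because of a drug-related event does not exclude.
- **Minimum exposure.** The same sentence also excludes a subject with fewer than 14 days at the target dose (3- or 4-week cycle) or 7 days (2-week cycle). It has no exception for drug-related events.
- **Restart.** Protocol Section 3.4 says of a subject who, after interruptions, is unable to "complete 2 repeat cycles for reasons other than DLT, the subject will not be DLT evaluable and can be replaced". SAP Section 6.2 repeats the exclusion: "if a subject is unable to complete 2 repeat cycles for reasons other than DLT, the subject will not be DLT evaluable". Protocol Section 6.2.1.5 has the parallel rule for two failed restarts, "the subject will be considered as not DLT evaluable (if no DLT has been observed during treatment) and can be replaced", and adds that the subject may "continue treatment with a previously tested target dose that has been well tolerated".

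On the consequence, the footnote to Protocol Table 5 reads "Subjects who are not DLT-evaluable (see Section 3.4) are excluded from the count of subjects". Mandated cohort sizes in Groups 2 and 3 are in evaluable subjects (Section 3.1.4). The final MTD/RP2D estimate uses DLT-evaluable subjects (Section 3.1.5), and so does the DLT analysis (Section 10.1.2; SAP Section 9.6.2). No cap on replacements is stated. Sections 3.4 and 6.2.1.4 do require the dose level review meeting (DLRM) to consider the safety data of non-evaluable subjects.

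**The concern.** The same AMG 330 event is handled in two ways. If the subject drops out, the dropout clause does not exclude. If the subject tries again twice and fails, the restart clause does.

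CRS, which the protocol calls a frequent toxicity (Section 2.1.3), fits this gap. On duration, "Grade 2 CRS that does not resolve, with or without intervention to Grade 1 within 7 days will be considered a DLT"; grade 2 CRS that clears sooner and comes back does not meet that criterion. Nor does a single grade 3 CRS above the initial dose that resolves within the 5- and 7-day limits. Either can still interrupt the infusion (Section 6.2.1.5). Under Table 6, more than 24 hours off drug means repeating the cycle: at any dose in a 2-week cycle, and at a run-in or step dose in a 3- or 4-week cycle.

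A subject who repeatedly loses the cycle this way has shown that the tested schedule could not be sustained. That subject then leaves the calculation that names the tolerated dose. Evaluating tolerability and estimating the MTD are both primary objectives, so the reason for exclusion is tied to the quantity being studied.

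**Working it through.** **The plan's own figures.** Protocol Section 10.2 gives the chance of at least one DLT at true rates of 10% to 33%. With 1 − (1 − p)^n:

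- n = 3: 1 − 0.9³ = 27.1% and 1 − 0.67³ = 69.9% (stated 27–70%).
- n = 6: 1 − 0.9⁶ = 46.9% and 1 − 0.67⁶ = 91.0% (stated 47–91%).

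Both reproduce. They allow for no non-evaluable fraction.

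**Inputs.** Let d be the share of treated subjects with a DLT. Let t be the share who fail two restarts from AMG 330 toxicity without a DLT. Neither is in the documents; d = 10% and t = 20%, 30% and 40% are assumptions. No other source of non-evaluability is modelled.

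**Counted event rate r under three treatments of the failures.**

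- Excluded and replaced (the plan): r = d/(1 − t).
- Kept in the denominator as no DLT: r = d.
- Counted as events: r = d + t.

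The plan's rate is at or above d. It lies below d + t whenever some subjects complete, because d/(1 − t) < d + t reduces to t(1 − d − t) > 0.

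**3+3 rule (Table 5).** Escalate on 0 of 3, or on 1 of 3 followed by 0 of the next 3:

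P(escalate) = (1 − r)³ + 3r(1 − r)² × (1 − r)³.

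| t | Excluded: r, P | Kept as no DLT: r, P | Counted as events: r, P |
|---|---|---|---|
| 20% | 12.5%, 86.2% | 10%, 90.6% | 30%, 49.4% |
| 30% | 14.3%, 82.8% | 10%, 90.6% | 40%, 30.9% |
| 40% | 16.7%, 78.0% | 10%, 90.6% | 50%, 17.2% |

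Example at t = 40% under exclusion: r = 0.10/0.60 = 0.167, and P = 0.579 + 0.201 = 0.780. Filling three evaluable places then takes 3/0.60 = 5 subjects on average.

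**mTPI-2 table (SAP Section 3.3), single look at n = 6.** The table escalates on 0 or 1 DLT, so P(E) = (1 − r)⁶ + 6r(1 − r)⁵. At d = 10% and t = 30% this is 79.3% under exclusion, 88.6% if kept as no DLT, and 23.3% if counted as events.

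**The case against.** A reader might infer that the rule biases the MTD upward, or that it lets a dose be escalated that most subjects cannot stay on. The documents do not support either statement. The MTD is defined by DLT incidence (Protocol Sections 3.1.1 and 3.1.4). Against that definition, exclusion raises the counted rate from d to d/(1 − t) and is less permissive than keeping these subjects as no DLT. The large gap appears only when failures are relabelled as events, which is a different endpoint. The failure rates are assumed, and the largest used here is 40%, not a majority.

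The pathway is also narrow. Grade 4 CRS, two grade 3 CRS events, grade 3 CRS at the initial MTD, unresolved grade 2 or 3 CRS and most grade 3–5 non-hematologic toxicity are already DLTs. Grade 2 CRS goes through continued dosing and a dose reduction before interruption. In longer cycles, an interruption of less than 7 days at the target dose does not automatically repeat the cycle.

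Safeguards exist. DLRM review of non-evaluable subjects is mandatory. The dose level review team (DLRT) can unanimously declare a DLT for a related event outside the window, which may cover repeat cycles. Enrollment can be suspended on safety findings (Section 10.3.1). The SAP tabulates events leading to interruption, CRS by grade, and cycles completed (Sections 9.6.3 and 9.6.9).

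All of this stands, and it limits the point without removing it. The review has no threshold and enters no estimate. The specific provision for non-DLT toxicities in Section 10.3.2 begins at grade 3, although adverse events in general are among the data reviewed. The DLRT reclassification does not reach events inside the window. None of the SAP tables is linked to evaluability or to the MTD estimate.

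**Conclusion.** The concern holds in a limited form. Restart failures caused by AMG 330 toxicity short of a DLT are removed from the counts behind the dose decisions and the MTD. The removal is informative and can overstate the tolerated dose by a tolerability standard. It does not bias the protocol-defined DLT rate downward.

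At an assumed 10% DLT rate and 20% to 40% such failures, the 3+3 escalation probability is 86% to 78% as planned. The two ways of keeping these subjects bracket it: 91% as non-events, and 49% to 17% as events. The width of that bracket shows how much could be hidden; it does not estimate what happened in this trial. The actual failure share is unknown from the documents, and the breadth of the DLT definition may keep it small. What is missing is any prespecified display of the exclusion, together with consistent wording of the clauses that produce it.

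**What to change.** 1. Reconcile the dropout, minimum-exposure and restart clauses across Protocol Sections 3.4, 6.2.1.4 and 6.2.1.5 and SAP Section 6.2, and state how a drug-related cause is treated in each. Section 6.2.1.5 also needs internal reconciliation: for a 2-week cycle its text gives a 10-day minimum at the target dose and its table gives 7 days. Copying the dropout wording into the restart clause would not be enough. The minimum-exposure clause would still exclude many of these subjects, and any who became evaluable would enter as non-events.
2. In the SAP and for each DLRM, tabulate non-evaluable and replaced subjects by cause and dose, beside the DLTs.
3. Prespecify a sensitivity version of the 3+3 or mTPI-2 decision, and of the final MTD or isotonic estimate, with AMG 330-related restart failures counted as events.

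The primary DLT definition and the escalation rule stay unchanged; making these failures formal events would redefine a DLT and is a separate debate. The cost is wording, one table and one calculation on data already collected. The downside is a less favourable tolerability picture at some doses.
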